3.4. RANDOMIZATION

Two strata will be considered based on albuminuria levels:

- High albuminuria (30-300 mg/g creatinine)
- Very high (>300 mg/g creatinine)

Patients will be randomized to either dapagliflozin or placebo in a 2:1 ratio.

Figura 2.-Randomization scheme

Total number of patients: 225; distributed as:

- 150 diabetic patients treated with dapagliflozin (10mg/day in a single dose), half of them with high albuminuria levels (albuminuria 30-300 mg/g of creatinine) and half with very high albuminuria levels (albuminuria > 300 mg/g of creatinine)

- 75 diabetic patients treated with placebo, half of them with high albuminuria levels (albuminuria 30-300 mg/g of creatinine) and half with very high albuminuria levels (albuminuria > 300 mg/g of creatinine)

Randomization will be stratified by albuminuria strata and participating hospital (three hospitals); center specific randomization lists (active treatment or placebo) will be prepared centrally at the project office with a treatment code assigned to each patient.

Allocation will be concealed by means of sequentially numbered, opaque, sealed envelopes that contain the medication code assigned. The envelopes have to be opened sequentially and only after the participant's name is written on the appropriate envelope.

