3.5. DRUG UNDER EVALUATION. BLINDING AND RELABELLING OF THE MEDICATION

The investigational medicinal product (IMP) is dapagliflozin 10 mg given once daily (film coated tablets, oral use).

The comparator will be placebo matching dapagliflozin 10 mg.

Either dapagliflozin or placebo will be administered through out the planned intervention period of the study (12 weeks).

AstraZeneca will donate both dapagliflozin 10 mg and placebo resembling dapagliflozin 10 mg for the study.

Identity of investigational product(s)

Investigational product	Dosage form and strength	Manufacturer
Dapagliflozin	10 mg, Green, plain, diamond shaped, film coated tablet (orally)	AstraZeneca
Matching placebo for dapagliflozin	Green, plain, diamond shaped, film coated tablet (orally). Does not contain active ingredient	AstraZeneca

Primary packaging of the Investigational Medicinal product (IMP) will be carried out by AstraZeneca or their designee in accordance with Good Manufacturing Practice (GMP).

Unlabeled bottles (identical) containing 35 tablets of each IMP will be provided by AstraZeneca.

The tablets contain lactose, which may cause discomfort in lactose-intolerant individuals.

Label, storage and distribution are a promotor's responsibility.

Preparation and labelling of Investigational Medicinal Product

To allow for adequate treatment for the diabetes, only participants will be blinded to the treatment they receive. Attending physicians will know the group in which every patient is. To preserve blinding for the patient, the study medication (active and placebo) will be sent from AstraZeneca to a certified company (LogistaPharma), where, in coordination with the CRO of the study [ODDS, S.L.], it will be counted, labeled and distributed to the participating centers. The IMPs will be labelled in accordance with Good Manufacturing Practice (GMP) and local regulatory guidelines for labeling. The labels will fulfill GMP Annex 13 requirements for labelling.

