LogistaPharma will send labeled medication with the corresponding randomization codified list to Hospital 12 de Octubre (Pharmacy Service). The investigator coordinator of the trial will distribute the medication **to** the primary care investigators. The study is single blinded, every investigator in each of the sites will have the randomization list with the individual treatment codes for each individual patient. The unblinding for the patient must not be done unless in medical emergencies. If the codes are broken for an individual patient, the promotor must be notified and decision if the data should be excluded from the analysis must be done by the promotor

The patient will receive the labelled medication, and counting of the pills will be done in the following visits: week 4, week 8 and week 12. Patients will also receive the medication leaflet of dapagliflozin, as stated in the form "Information for the patient"

Storage

All study drugs will be kept in a secure place under appropriate storage conditions. The IMP label on the bottle specifies the appropriate storage.

At the end of the study, all the study medication that has not been used will be collected from the patients by the investigators to be properly destroyed.

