3.9. VISITS, VARIABLES AND MEASUREMENTS

Four clinical visits are planned in every patient at 0 (recruitment and randomization), 4, 8 and 12 weeks. Information on personal and family history of disease, clinical examination (including office BP determination), ABPM and blood and urine samples will be obtained on visits 0. The variables measured in the blood and urine samples depend on the criterium of the attending physician. For this trial, only HbA1c, serum creatinine, estimated glomerular filtration rate (eGFR) and albuminuria are mandatory. All this information, except personal and family history of disease, will also be collected at week 12 (see “3.20. Conduct of the study”). Thirty days after the end of the medication (visit of week 12) all participants will be contacted by telephone to assess safety. For the initial laboratory data required in the CRF, data obtained in primary care in the previous 3 months could be valid. These data will be repeated at the end of the study. Informed consents for the study will be signed by the patients before coming to the hospital. Blood samples extractions included in this protocol will be done, handled and analyzed at each clinical setting according to usual clinical

practice. No blood sample storage will be needed in this study. Extra blood samples drawn will be handled as described in “3.23. Addendum”.

The relationship of the procedures performed at every clinical visit is presented below (see “3.20. Conduct of the study”). Case report forms (CRFs) are presented in Annex I. Albuminuria will be measured according to generally used and previously described methodologies(18-23).

ABPM will be measured using Mobil-o-Graph that will give us 24 hours brachial and central BP as well as pulse wave velocity and heart rate(24). As diary of activity of the patient will not be recorded, in this study, nocturnal (or nighttime) blood pressure refers to measurements within the period from 12.00 p.m. to 6.00 a.m.

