3.10. WITHDRAWAL OF PATIENTS FROM THE STUDY AND UNBLINDING

Any patient can be withdrawn from the study at anytime during follow-up based on medical criteria of attending physician. The latter will detail the reasons of the withdrawal and communicate it urgently to the coordinating office of the trial if needed. If the reason for withdrawal is an adverse event (AE), the patient will be followed according to the procedures described for AEs (3.16).

Any patient can decide to abandon the study at any time during the study.

Withdrawal from the trial for any reason is definitive. When leaving the study, the main reason will be recorded and, if possible, the patient should have a final exam with the content of the visit of week 12. Patients that abandon the study will not be substituted.

All the above mentioned situations cause unblinding of the study. The primary care physician is always aware of the medication that receives the patient (single blind) and

will be the contact person and responsible to break the blind. Contact details are available in the patient information form. After unblinding, the responsible primary care physician will report it to the coordinating office of the project (ODDS, S.L., [contact]).

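### Section 3.4 conceals allocation in sealed envelopes, but section 3.5 gives every investigator the randomization list without limiting it to patients already assigned

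*Combined protocol and SAP*

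**What the plan says.** Section 3.4 (Randomization) sets the concealment rule: "Allocation will be concealed by means of sequentially numbered, opaque, sealed envelopes that contain the medication code assigned". It adds that "The envelopes have to be opened sequentially", each only once the participant's name is on it. The same section describes where the sequence comes from: "center specific randomization lists (active treatment or placebo) will be prepared centrally at the project office with a treatment code assigned to each patient".

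Section 3.5 (Drug under evaluation) makes the study single blind, with only the patient unaware of treatment, and says: "Attending physicians will know the group in which every patient is". Later in the section it states that "every investigator in each of the sites will have the randomization list with the individual treatment codes for each individual patient". It also has the labelling company send a coded randomization list with the labelled medication to the pharmacy of one hospital.

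Section 3.10 (Withdrawal and unblinding) repeats that the primary care physician knows what the patient is taking, and makes that physician responsible for breaking the blind.

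On the order of events, section 3.9 says: "Informed consents for the study will be signed by the patients before coming to the hospital". The visit table in 3.20 puts eligibility and consent in primary care. It puts randomization and drug distribution at the hospital, within 7 days of the primary care visit.

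**The concern.** Sealed envelopes protect a trial only if the people who decide whether and when a patient is randomized cannot learn the next assignment in another way. A list of codes and arms in their hands would be such a way. The envelopes are the only concealment measure the plan states, and with physicians unblinded nothing else separates enrolment decisions from knowledge of the arm.

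If a person who randomizes could see what comes next, a consented patient could be put before or after another, held back, or not randomized, according to the arm due. The groups would then differ for reasons other than chance. Section 3.13 provides comparability tests and, if needed, linear regression for confounders. Both work only on what was measured, and neither can bring back a patient who was never randomized.

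**Working it through.** No arithmetic applies. The check is to set the statements side by side and ask what must be true for a list-holder to foresee an assignment.

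**Four conditions, all needed**

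1. *The list covers positions not yet used.* Section 3.5 does not say. It gives no release time and no restriction to assigned patients. The lists in 3.4 are prepared centrally, with a code assigned to each patient, and envelopes numbered in sequence imply that they exist before enrolment. That 3.5 means the same lists is suggested by the shared term but not stated.
2. *The list shows the arm, or lets it be worked out.* The lists in 3.4 show active treatment or placebo. Section 3.5 mentions treatment codes. Physicians are to know the group while the envelope holds only the code, so something available to them must link code to group.
3. *The list shows the order of codes in the envelopes.* Section 3.5 does not say. A list in the sense of 3.4 would normally carry the order. A plain key from code to group need not.
4. *The holder has some control over randomization.* Section 3.5 says every investigator in each site. By 3.20, randomization takes place at the hospital after consent in primary care. The document does not say who opens the envelopes. Read literally, hospital investigators are among the list-holders.

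On the literal reading, with the term used as in 3.4, all four conditions can be met by hospital staff. No sentence in the document rules that out.

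**The list sent with the medication.** Because 3.20 places randomization and drug distribution at the same hospital visit, the medication and its list would probably reach the pharmacy before the patients concerned are randomized. This is an inference. The document does not say whether that list shows groups, or whether it is the one investigators hold.

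**Does single blinding require the list in advance?** No. The reason given in 3.5 for unblinded physicians is adequate treatment of the diabetes, and 3.10 concerns the medication a patient is receiving. Both are met if the physician learns the group of his or her own patient once it is assigned. Envelopes and unblinded physicians are compatible; envelopes and an unrestricted list are not.

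**The case against.** The strongest reply is that the sentence in 3.5 describes a decoding key. The envelopes contain a code and not a group, so the plan cannot give physicians the group without a key. The wording speaks of individual codes for individual patients, and the next sentences deal with breaking the code. A key that covers every code, even unused ones, would not reveal the next assignment unless it also gave the envelope order, and 3.5 does not say that it does.

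A second reply concerns who holds the list. The sentence directly follows one about passing medication to primary care investigators, and 3.10 makes the primary care physician responsible for unblinding. If the list is held only in primary care, its holders do not randomize, and the document does not show that they know the position reached in any sequence.

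Both replies stand as possible readings, and they limit the claim. A reader might infer that concealment is bound to fail, that primary care recruiters can foresee assignments, or that single blinding itself contradicts the envelopes. The document supports none of these: it shows no disclosure of coming assignments, gives recruiters no view of the sequence, and needs physician knowledge only after assignment. But neither reply is written into the plan, and the shared term in 3.4 points the other way. A site that follows 3.5 as worded would be within the protocol in holding the full list.

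**Conclusion.** The point holds as an unreconciled inconsistency. Section 3.4 seals the allocation; 3.5 hands out a list that, on a literal reading, could unseal it for anyone who also randomizes patients. The milder readings (a key without envelope order, a key for assigned patients only, or a list held only by primary care investigators who do not open envelopes) remain open.

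No size can be attached. The document gives no basis for how often selection would occur or how far it would move nocturnal blood pressure, so any percentage would rest on assumptions alone. The sample size in 3.11 (150 and 75) is not affected.

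This should be fixed. The assessment rests on a stated rule that could defeat a stated safeguard, on harm that the analysis cannot fully repair, and on a cheap remedy. It should be rated more serious if the sponsor confirms that the investigators' list covers unassigned positions in order. If the sponsor confirms a key for assigned patients only, what remains is a clarification of wording.

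**What to change.** Ask the sponsor which list the investigators hold, whether it covers unassigned positions, and whether it shows their order.

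In 3.5, keep the statement that the study is single blinded and replace the rest of that sentence with:

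> No one who recruits patients, randomizes them or opens envelopes has access to the treatment group, or to the order of codes, for patients not yet randomized. After a patient's envelope is opened, the code and treatment group of that patient are released to the hospital investigator and to the patient's primary care physician by the project office.

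In 3.4, state that eligibility and albuminuria stratum are recorded before the envelope is opened.

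The cost is a small procedural step at three hospitals to release each patient's group after assignment. The second sentence of the new text settles how the primary care physician, who is not at the hospital when the envelope is opened, learns the group. Physician knowledge after assignment and emergency access are kept. No patients, visits or analyses are added.

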3.6. DRUGS NOT PERMITTED DURING THE CLINICAL TRIAL

While in the clinical trial, this protocol does not permit the use of the following drugs and/or changes in medication:

- Loop diuretics.
- SGLT2 inhibitors.
- Pioglitazone

If the attending physician considers that for the best care of the patient the use of any of the above mentioned drugs or changes in treatment is absolutely essential, the patient will be withdrawn from the study, the blinding for the patient will be broken and the promotor informed.

Any other change in medication which does not lead to withdrawal from the study will be recorded in the CRD.

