3.13. PLAN OF ANALYSIS

The main analysis will compare baseline and final visit values of nocturnal blood pressure and all the rest of quantitative variables of interest within each stratum of albuminuria by means of paired t-test. Changes of nighttime blood pressure from baseline to final visit among patients with high and very high albuminuria levels will be compared to placebo with t-test.

Variables will be described by means of mean (and standard deviation) or proportion depending on the type of variable considered. Whenever the test of hypothesis may involve discrete variables, chi-squared test will be used.

Comparability of treatment and placebo groups will be tested (t-student or chi-squared test, depending on the variable) to assess randomization, and linear regression will be used to adjust for potential confounders, if needed; stratum of albuminuria at randomization will be forced in the model.

To respond to secondary objectives, the same analyses will be done for each stratum of albuminuria at randomization.

Only patients that complete the 3-month follow-up will be analyzed. Patients who do not complete the follow-up will be compared to those who adhere to the protocol.

No interim analysis is planned. A *p* value<0.05 will be considered as statistically significant.

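### After a code break, Section 3.5 lets the promotor decide, without criteria and with nothing to keep the decision blind, whether the patient's data are analysed

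*Combined protocol and SAP*

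**What the plan says.** All references are to the combined protocol and SAP.

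- **Section 3.5 (blinding), exclusion.** If an individual code is broken, the promotor is notified and the "decision if the data should be excluded from the analysis must be done by the promotor". No criteria, timing or reviewer are named.
- **Section 3.5, when a code may be broken.** "The unblinding for the patient must not be done unless in medical emergencies".
- **Section 3.5, who is blinded.** The text states that "only participants will be blinded to the treatment they receive", and that "every investigator in each of the sites will have the randomization list with the individual treatment codes for each individual patient".
- **Section 3.6 (drugs not permitted).** If a prohibited drug or treatment change becomes essential, "the patient will be withdrawn from the study, the blinding for the patient will be broken and the promotor informed".
- **Section 3.10 (withdrawal).** "Any patient can be withdrawn from the study at anytime during follow-up based on medical criteria of attending physician"; patients may also leave by choice. An exit examination with week-12 content is to be done where possible. Of all these cases the section says: "All the above mentioned situations cause unblinding of the study".
- **Section 3.13 (analysis).** "Only patients that complete the 3-month follow-up will be analyzed". The section does not mention the promotor's decision, and it defines no all-randomised set and no sensitivity analysis.

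**The concern.** A decision taken after randomisation about whose data count should follow a written rule, or be made by someone who knows neither arm nor result. Section 3.5 provides neither safeguard.

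Code breaks are unlikely to occur at random. They follow emergencies, a need for prohibited treatment, or withdrawal, including withdrawal for an adverse event. All of these are plausibly related to treatment and to blood pressure, and the physicians who trigger many of them know the arm.

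The plan gives no reason for exclusion. The primary endpoint comes from an ambulatory monitor (Section 3.9), and a patient learning the arm does not in itself invalidate a reading.

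At stake is whether the set of patients in the primary comparison is fixed by the protocol or can be altered case by case. Removing poor responders from the active arm would exaggerate the effect; removing good responders would dilute it.

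**Working it through.** **Step 1. Whom the discretion reaches.** Sections 3.5 and 3.13 side by side:

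| Patient | Section 3.13 | Section 3.5 | Outcome |
|---|---|---|---|
| Code not broken, completes week 12 | Analysed | Not engaged | Analysed |
| Code broken, completes week 12 | Analysed | Promotor may exclude | Undetermined; the sections can contradict each other |
| Withdrawn, no exit examination | Not analysed | Nothing left to decide | Out by the fixed rule |
| Withdrawn, exit examination done | Not stated whether this counts as completing | Promotor may exclude | Undetermined |

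Only the second and fourth rows are open. The documents give no expected number for either.

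**Step 2. The plan's own figure.** Inputs from Section 3.11: two-sided alpha 0.05, power 80%, difference 5 mmHg, SD 12 mmHg (taken here as the SD of the change), 2:1 allocation, 9% drop-out.

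- Placebo: (1.960 + 0.842)² × 12² × (1 + 1/2) / 5² = 67.8, so 68. Active: 2 × 68 = 136.
- Inflated for drop-out: 68 / 0.91 = 74.7, so 75; 136 / 0.91 = 149.5, so 150. The stated 75 and 150 reproduce.
- Standard error of the difference with 68 and 136 evaluable patients: 12 × √(1/68 + 1/136) = 1.78 mmHg.

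**Step 3. Size of the bias, under assumptions.** Let a fraction f of one arm's otherwise analysable patients be removed, and let their mean change differ by D from that of the retained patients. The arm mean then shifts by f × D. Neither f nor D is in the documents. The ranges assumed are f from 1% to 9% (about 1 to 12 of 136 active patients) and D from 5 to 12 mmHg.

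As an upper bound, suppose the removed patients are exactly the most extreme responders in that arm. For a normal distribution the shift is then SD × φ(z_f) / (1 − f), with z_f the normal quantile at f. Two-sided type I error is approximated as 1 − Φ(1.96 − b/1.78) + Φ(−1.96 − b/1.78), where b is the shift and the standard error is held at 1.78.

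| f | Shift, D = 5 | Shift, D = 12 | Type I error, D = 12 | Upper-bound shift | Type I error at the bound |
|---|---|---|---|---|---|
| 1% | 0.05 mmHg | 0.12 mmHg | 0.051 | 0.32 mmHg | 0.054 |
| 5% | 0.25 mmHg | 0.60 mmHg | 0.063 | 1.30 mmHg | 0.113 |
| 9% | 0.45 mmHg | 1.08 mmHg | 0.093 | 2.14 mmHg | 0.225 |

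The assumed range therefore gives 0.05 to 1.08 mmHg, which is 1% to 22% of the 5 mmHg target.

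**The case against.** The best defence is that Section 3.13 does most of the work. Withdrawal is definitive under Section 3.10 and non-completers are not analysed, so for most withdrawn patients the promotor has nothing to decide. This stands. A reader might infer that, because every withdrawal counts as an unblinding, all expected drop-outs (0.09 × 225 = 20.25, about 20 patients) are open to discretionary exclusion. The documents do not support that: those patients mostly leave by the fixed rule and are already allowed for in the sample size. The completers-only rule can itself bias the comparison, but that is a different defect.

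Second, code breaks among completers may be rare or absent, and serious inflation of the error rate needs 5% to 9% of an arm to be selected on outcome. This also stands. A reader might conclude that the p-value loses all protection; at 1% removal the error rate stays near 0.05 even in the upper bound.

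Third, no passage says that the promotor knows the arm. That is correct. But the stated blind covers participants only, and no step keeps arm or result from whoever decides.

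Fourth, the emergency-only rule in Section 3.5 may be meant for patients still in the study, with Sections 3.6 and 3.10 governing exit. That is a fair reading, but the text does not say so, and the conflict between Sections 3.5 and 3.13 over unblinded completers remains.

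Finally, a patient who learns the arm might change behaviour before the final reading. That could justify a prespecified sensitivity analysis; it does not justify an exclusion decided case by case.

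**Conclusion.** The point holds within limits. Section 3.5 is an explicit rule that allows exclusion after randomisation without criteria or timing, and without protection from knowledge of arm or outcome. It leaves the analysis set undetermined for unblinded completers and, arguably, for withdrawn patients with an exit examination.

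The size cannot be derived from the documents. The 0.05 to 1.1 mmHg range rests on assumed values of f and D and on removal from one arm only, and the true effect may be close to zero. The case for change rests on the discretion being uncontrolled and easily removed, not on a demonstrated large bias. No change to the sample size follows.

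**What to change.** 1. Delete the promotor's exclusion decision from Section 3.5.
2. State in Sections 3.5 and 3.13 that a code break is recorded as a deviation and never by itself removes a patient. Every randomised patient with a baseline and a week-12 ABPM is then analysed in the assigned arm.
3. State in Section 3.13 whether patients with an exit examination under Section 3.10 count, for example in a sensitivity analysis. This keeps the primary endpoint at week 12.
4. Allow any other exclusion only in a sensitivity set, with criteria written before database lock.
5. Reconcile the statements on unblinding in Sections 3.5, 3.6 and 3.10 with each other and with Section 3.13. Which unblinding rule should apply is for the sponsor and investigators to settle.

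The cost is protocol and SAP wording, plus at most a small sensitivity analysis on data already planned for collection. Patient numbers, visits and procedures do not change.
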